7.1. Primary Efficacy Analyses

7.1.1. Endpoint / Variables

- Change from baseline to the nadir (maximum change from baseline) in Plasma HIV-1 RNA
- Change from baseline to Visit 6 (Day 11 in Part 1 and Day 8 in Part 2) in Plasma HIV-1 RNA

7.1.2. Summary Measure

- Mean rate of maximum change from baseline to the nadir
- Mean rate of change from baseline to Visit 6 (Day 11 in Part 1 and Day 8 in Part 2)

7.1.3. Statistical Analyses / Methods

Statistical models will be fitted separately for Part 1 and Part 2.

Plasma HIV-1 RNA maximum change from baseline (on original scale and log₁₀ scale) and time to nadir will be calculated for each subject and summarized by treatment for each part.

Details of the planned displays are provided in [Appendix 11](#): List of Data Displays and will be based on GSK data standards and statistical principles.

Unless otherwise specified, endpoints / variables defined in Section [7.1.1](#) will be summarised using descriptive statistics, graphically presented (where appropriate) and listed.

7.1.3.1. Statistical Methodology Specification

Endpoint / Variables

 Change from baseline to the nadir in Plasma HIV-1 RNA (on log₁₀ scale) Change from baseline to Visit 6 (Day 11 in Part 1 and Day 8 in Part 2) in Plasma HIV-1 RNA (on log₁₀ scale)
Model Specification

 Plasma HIV-1 RNA change from baseline (on log₁₀ scale) to nadir and change from baseline to Visit 6 (Day 11 in Part 1 or Day 8 in Part 2) (on log₁₀ scale) will be fitted in a mixed-effects linear model by treatment, with baseline plasma HIV-1 RNA (on log₁₀ scale) and visit fitted as fixed effects and subject fitted as a random effect.
Model Checking & Diagnostics

 Model assumptions will be applied, but appropriate adjustments may be made based on the data.
Model Results Presentation

 Statistical analysis for maximum change from baseline to the nadir and change from baseline will be presented in tabular format. The linear model will be used to estimate slope, intercept and a 90% CI of the slope. The model will be fitted for Part 1 and Part 2 data respectively. 
Example SAS Code:
 <pre>proc mixed data=dataset; class dose visit subjid; model chgRNA = baseRNA visit dose; random subjid / type=un solution; run;</pre>
Sensitivity and Supportive Analyses
Both ITT and PP population will be used for the above analyses if PP population is differed from ITT population.

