10.3.2.2. Efficacy Analyses

Both the PP and ITT Populations will be used for all efficacy analyses if there are dropouts. Plasma HIV-1 RNA max change and change from baseline during the study will be calculated for each participant and on each assessment visit/day.

Plasma HIV-1 RNA will be listed by treatment, participant, and assessment visit/day and summarized by treatment and assessment visit along with change from baseline.

Plots of mean and median plasma HIV-1 RNA actual and change from baseline data will be generated by treatment and assessment visit.

- Plasma HIV-1 RNA change from baseline to the nadir (maximum change from baseline) will be calculated for each participant and summarized by treatment.

Together, the data from Parts 1 and 2 will investigate the complete dose-exposure-response curve and the impact of lower doses/exposures on potential development of resistance.

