2.3. Study Design

Overview of Study Design and Key Features	

The diagram illustrates the study design, divided into Part 1 and Part 2. Part 1 starts with N=14 participants randomized on Day 1. They are assigned to three groups: GSK3640254 200 mg once daily (N=6), GSK3640254 10 mg once daily (N=6), and PLACEBO (N=2). Part 2 starts with N=20 participants randomized on Day 1. They are assigned to four groups: GSK3640254 Dose 90% Max Effect 140 mg (N=6), GSK3640254 Dose 75% Max Effect 80 mg (N=6), GSK3640254 Dose 30% Max Effect 40 mg (N=6), and PLACEBO (N=2). An unblinded interim analysis is conducted by the Study Team to confirm GO to Part 2 and refine Part 2 doses as needed. The timeline shows Day 1 Randomization, Follow-up at Day 10 for Part 1, and Day 1 Randomization, Follow-up at Day 7 for Part 2.
	
Design Features	
 This is a Phase 2a, global, multicentre, randomized, double-blind (Sponsor-unblinded), placebo-controlled, adaptive clinical trial to evaluate the antiviral effect, safety, tolerability and PK/ pharmacodynamics (PD) of GSK3640254 over 10 days in study Part 1 and over 7 days in study Part 2 in ART naïve HIV-1 infected adults, who are termed “participants” in the study. All participants will be screened for eligibility before being randomized, preferably within 14 days, into a 10-day treatment period in Part 1 and into a 7-day treatment in Part 2. The 14-day screening period may be extended to 28 days in some cases to allow receipt of all screening results and/or to accommodate scheduling.
Dosing	
 Part 1 will include approximately 14 randomized participants and will evaluate two active doses of GSK3640254, 200 mg once daily or 10 mg once daily, in cohorts of 6 participants each for 10 days. A cohort of 2 participants will be randomized to receive placebo for 10 days. Part 2 will include approximately 20 randomized participants and will evaluate three active doses of GSK3640254, 140/80/40 mg once daily, in cohorts of 6 participants each for 7 days. A cohort of 2 participants will be randomized to receive placebo for 7 days.
Time & Events	
 See Appendix 2: Schedule of Activities for additional details of activities
Treatment Assignment	
 All participants will be centrally randomized using an Interactive Voice/Web Response System (IVRS/IWRS).

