13.11.5. Efficacy Tables

Efficacy: Tables					
No.	Population	IDSL / Example Shell	Title	Programming Notes	Deliverable [Priority]
Plasma HIV-1 RNA (ITT)					
2.1.	ITT	EFF_T1	Summary of Plasma HIV-1 RNA – Part 1	On original and log10 scale	SAC
2.2.	ITT	EFF_T1	Summary of Plasma HIV-1 RNA – Part 2	On original and log10 scale	SAC
2.3.	ITT	EFF_T2	Summary of Change from Baseline to Nadir and Change from Baseline to Visit 6 (Day 11) in Plasma HIV-1 RNA – Part 1	On original and log10 scale	SAC
2.4.	ITT	EFF_T2	Summary of Change from Baseline to Nadir and Change from Baseline to Visit 6 (Day 8) in Plasma HIV-1 RNA – Part 2	On original and log10 scale	SAC
2.5.	ITT	EFF_T2	Summary of Time to Nadir in Plasma HIV-1 RNA – Part 1		SAC
2.6.	ITT	EFF_T2	Summary of Time to Nadir in Plasma HIV-1 RNA – Part 2		SAC
2.7.	ITT	EFF_T3	Summary of Modelled Plasma HIV-1 RNA Mean Rate of Change from baseline to Visit 6 (Day 11) and Maximum Change by Treatment – Part 1	On log10 scale	SAC
2.8.	ITT	EFF_T3	Summary of Modelled Plasma HIV-1 RNA Mean Rate of Change from baseline to Visit 6 (Day 8) and Maximum Change by Treatment – Part 2	On log10 scale	SAC
2.9.	ITT	EFF_T4	Summary of Proportion of Participants with Plasma HIV-1 RNA <400 and < 50 copies/mL – Part 1	By visit and by treatment	SAC

CONFIDENTIAL

208132

Efficacy: Tables					
No.	Population	IDSL / Example Shell	Title	Programming Notes	Deliverable [Priority]
2.10.	ITT	EFF_T4	Summary of Proportion of Participants with Plasma HIV-1 RNA <400 and < 50 copies/mL – Part 2	By visit and by treatment	SAC
2.11.	ITT	EFF_T5	Summary of Proportion of Participants with Plasma HIV-1 RNA Change from Baseline >1.5 log ₁₀ copies/mL Decrease -Part 1	By visit and by treatment	SAC
2.12.	ITT	EFF_T5	Summary of Proportion of Participants with Plasma HIV-1 RNA Change from Baseline >1.5 log ₁₀ copies/mL Decrease -Part 2	By visit and by treatment	SAC
Immunology (ITT)					
2.13.	ITT	EFF_T6	Summary of CD4+ and CD8+ and Change from Baseline by Visit – Part 1	Please include both absolute CD4 count and CD4 percentage, Same to CD8	SAC
2.14.	ITT	EFF_T6	Summary of CD4+ and CD8+ and Change from Baseline by Visit – Part 2	Please include both absolute CD4 count and CD4 percentage, same to CD8	SAC
2.15.	ITT	EFF_T3	Summary of Modelled CD4+ Cell Count Mean Rate of Change from baseline to Visit 6 (Day 11) by Treatment – Part 1	On log ₁₀ scale	SAC

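### The model for change to nadir includes a visit term and a random subject effect that do no useful work on one record per participant, and the SAP does not say what visit means on that record

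*SAP*

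**What the plan says.** Protocol Section 10.3.2.2 defines the endpoint at participant level: "Plasma HIV-1 RNA change from baseline to the nadir (maximum change from baseline) will be calculated for each participant and summarized by treatment". SAP Section 7.1.1 lists it as the first primary variable, "Change from baseline to the nadir (maximum change from baseline) in Plasma HIV-1 RNA", next to change from baseline to Visit 6.

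SAP Section 7.1.3.1 gives both variables the same model on the log10 scale: baseline HIV-1 RNA and "visit fitted as fixed effects and subject fitted as a random effect". The example code lists dose, visit and subject as class variables and has "model chgRNA = baseRNA visit dose". The stated output is a slope, an intercept and a 90% CI for the slope. Section 7.1.3 adds that "Statistical models will be fitted separately for Part 1 and Part 2".

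Nadir timing is treated as an outcome in its own right. Section 7.1.3 says that "time to nadir will be calculated for each subject and summarized by treatment for each part", and Tables 2.5 and 2.6 report it.

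The modelled nadir result appears in Table 2.7, "Summary of Modelled Plasma HIV-1 RNA Mean Rate of Change from baseline to Visit 6 (Day 11) and Maximum Change by Treatment", in Table 2.8 for Part 2, in the per-protocol Tables 2.23 and 2.24, and in Listings 49 and 51. Nothing in Section 7 says what visit contains on a nadir record, or that the term is dropped for that endpoint.

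**The concern.** A visit effect and a random subject effect belong to repeated measures. The nadir is a single derived value, so the visit term has to take one of two forms.

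- **Visit at which the nadir occurred.** This is known only after randomisation and dose can influence it. Adjusting for it compares doses among participants whose nadir fell at the same visit. That is a different question from how far HIV-1 RNA fell on each dose.
- **A single constant label.** The term is then aliased with the intercept and contributes nothing.

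A programmer following Section 7.1.3.1 literally could produce the first. At stake is the modelled nadir result by dose in very small cohorts (6:6:2 and 6:6:6:2), where each extra visit level costs a degree of freedom and placebo can become confounded with visit.

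**Working it through.** **The plan's own figure.** The SAP states no operating characteristic for this model. The nearest design figure is protocol Table 5: with n = 6, SD 0.4 and true mean drop 1.3 log10, 81.8% of trials have posterior probability of at least 20%. Treating the SD as known, a trial passes if its observed mean exceeds 1.3 − 0.8416 × 0.4/√6, which at a true mean of 1.3 has probability 80.0%. Using the stated inverse-gamma prior for a single arm gives 81.3%. The figure reproduces, but it confirms only n and SD and does not bear on the visit term.

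**Inputs from the documents.** SAP Section 2.3: "Part 1 will include approximately 14 randomized participants and will evaluate two active doses of GSK3640254", allocated 6:6:2. Part 2 has 20 participants, allocated 6:6:6:2. The schedules of activities give 8 post-baseline HIV-1 RNA visits in Part 1 (Visits 2-9) and 6 in Part 2 (Visits 2-7), or 5 if Part 2 is cut at Day 8.

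**Residual degrees of freedom**, with k distinct nadir visits occurring:
- Part 1 without visit: 14 − 3 doses − 1 baseline = 10. With visit: 10 − (k − 1). For k = 3 to 5 this is 8 to 6.
- Part 2 without visit: 20 − 4 − 1 = 15. With visit and a Day 8 cut, the simulated average was about 12.7.

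**When placebo cannot be compared.** If both placebo nadirs fall at visits that no active participant shares, the placebo effect is confounded with visit. With a flat placebo profile and independent sampling error, each post-baseline visit is equally likely to be the placebo nadir. If active nadirs occupy m of V visits, the probability is ((V − m)/V)².
- Part 1, V = 8: m = 4 gives (4/8)² = 25%; m = 3 gives (5/8)² = 39%.
- Part 2 to Day 8, V = 5: m = 3 gives (2/5)² = 16%; m = 2 gives (3/5)² = 36%.

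**Simulation.** Each scenario had 4,000 to 6,000 trials. Assumed, not in the documents: active-arm drops 0.7-1.7 log10, between-participant SD about 0.3, within-participant SD 0.1-0.3, flat placebo, partial rebound after dosing. With one record each, the subject variance merges with the residual, so the fixed effects equal ordinary least squares. Visit is coded as the nadir visit. Results are for top dose minus placebo, in log10.

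| Setting | Mean, no visit → visit | SD, no visit → visit | Not estimable with visit |
|---|---|---|---|
| Part 1, dose does not shift timing | −1.35 → −1.28 | 0.25 → 0.43 | 32% (24-48% for within-participant SD 0.3-0.1) |
| Part 1, lower dose reaches nadir earlier | −1.39 → −1.17 | 0.32 → 0.60 | 17.5% |
| Part 1, stronger timing shift | −1.47 → −1.14 | 0.32 → 0.67 | 18.8% |
| Part 2 to Day 8, dose does not shift timing | −1.11 → −1.01 | 0.25 → 0.38 | 22% |
| Part 2 to Day 8, lower doses earlier | −1.28 → −1.02 | 0.28 → 0.46 | 8.8% |
| Part 2, Visit 7 counted | −1.29 → −1.27 | SE ratio 1.00 | 1.5% |

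**Attenuation.** Without a timing shift it is 1 − 1.28/1.35 = 5% in Part 1 and 1 − 1.01/1.11 = 9% in Part 2. A second set of assumed trajectories gave 2% and 5%. With a timing shift it is 16% and 22% in Part 1 and 20% in Part 2. In those two Part 1 scenarios the top-versus-low-dose difference shrank by 23% and 51%.

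**After the fix.** Every dose contrast is estimable, residual degrees of freedom are 10 and 15, and the SD is 0.25 in both parts in the scenarios without a timing shift.

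**The case against.** The strongest reply is that the SAP never says the model runs on one record per participant. Section 7.1.2 speaks of a mean rate, Section 7.1.3.1 asks for a slope and fits a random subject effect, and the code is only an example that allows data-based adjustment. All of this suggests several records per participant with visit as the time axis. The mock shells in Appendix 12, which might settle the layout, are not in the public text, and their absence cannot be held against the plan.

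That stands as a reason not to call the result wrong. It does not rescue the term. Several records up to the nadir would no longer be the per-participant maximum change that the protocol defines, and visit as a class variable still yields no slope.

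Other parts of the reply do stand:
- Section 7.1.3.1 has no adjusted-mean or contrast statement, and Section 2.4 says no formal hypothesis is tested. The placebo difference used above measures the damage and is not a planned output. With two placebo participants per part it is fragile under any model.
- Section 7 sets no Day 8 cut, and Section 10.1.4 says the descriptive maximum change uses all visits. If that carries over to this model, Part 2 is almost unharmed.

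**Conclusion.** The point holds as a specification defect in SAP Section 7.1.3.1. For change to nadir, the visit term either conditions on a post-randomisation outcome or does nothing, and the random subject effect is not separable from the residual.

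Under the nadir-visit coding and the assumed trajectories, the robust consequences in Part 1 are lost estimability and lost precision. The top-dose-minus-placebo difference is not estimable in roughly 24-48% of trials when dose does not shift timing (about 18-19% in the scenarios where it does). Its SD rises by a factor of 0.43/0.25 = 1.7. Attenuation is secondary, about 5-9% in the main scenarios, unless dose also shifts nadir timing. Part 2 shows the same pattern with a Day 8 cut and almost none of it if the post-cART Visit 7 counts.

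A reader might infer more than the documents support:
- **That no coding gives a valid adjusted mean.** A constant visit leaves the fixed effects as baseline plus dose, which is the model recommended here.
- **That this is the only model of maximum change.** Sections 10 and 11 fit Emax models to maximum change up to Day 8 without a visit term, and these are unaffected.
- **That the trial's nadir result is compromised.** The descriptive summaries in Tables 2.3 and 2.4, which deliver the protocol's stated analysis, do not depend on this model.
- **That the CD4 model is harmed in the same way.** CD4 has one scheduled post-baseline visit per part, so visit is constant there.

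**What to change.** For change to nadir, state that the analysis dataset has one record per participant. Fit, separately in each part, log10 maximum change = baseline log10 HIV-1 RNA + dose, with no visit term and no random subject effect. Report the adjusted mean for each dose with its 90% CI. Keep nadir timing only in the time-to-nadir summary.

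This is one line of SAP text and code and needs no new data. The small cost is consistency: for the nadir endpoint, the mean-rate, slope and intercept wording in Sections 7.1.2 and 7.1.3.1 and in the titles of Tables 2.7, 2.8, 2.23 and 2.24 must change to match. Removing visit from the CD4 model in Section 7.3.1.4, or from a model that uses only the Visit 6 change, is tidying that alters no estimate.

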7.3.1.2. Summary Measure

Descriptive summaries will include n, mean, standard deviation (SD), median, minimum, and maximum for continuous variables, whereas n and percent will be used as summary statistics for categorical variables.

In addition, mean rate of change for CD4+ T-cell count change from baseline to Visit 6 (Day 11 in Part 1 and Day 8 in Part 2) will be calculated based on the following linear mixed model.

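### The example code for the modelled HIV-1 RNA and CD4+ tables cannot produce the slope and 90% CI the SAP promises, and the mean rate named for nadir and CD4+ change is never defined

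*SAP*

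**What the plan says.** SAP 7.1.3.1 covers two HIV-1 RNA endpoints on the log10 scale: change to nadir and change to Visit 6 (Day 11 in Part 1, Day 8 in Part 2). The text says they "will be fitted in a mixed-effects linear model by treatment", names baseline and visit as fixed effects and subject as random, and then promises: "The linear model will be used to estimate slope, intercept and a 90% CI of the slope". Parts 1 and 2 are modelled separately.

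The example code beneath consists of these statements:

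- "class dose visit subjid"
- "model chgRNA = baseRNA visit dose"
- "random subjid / type=un solution"

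SAP 7.3.1.4 repeats the specification, the promised output and the code structure for CD4+ change to Visit 6.

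The summary measures are worded as rates. SAP 7.1.2 lists "Mean rate of maximum change from baseline to the nadir" and a mean rate for the Visit 6 RNA change. SAP 7.3.1.2 adds: "In addition, mean rate of change for CD4+ T-cell count change from baseline to Visit 6". The schedules in SAP Appendix 2 mark CD4/CD8 at Visits 1 and 6 only.

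**The concern.** The specification names an output that its own code does not contain. A programmer following it has to invent the time term, the interval request and the meaning of the rate. Those choices would be made after the sponsor has seen unblinded Part 1 data (SAP 3.1).

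The displays that depend on it are Tables 2.7, 2.8, 2.15 and 2.16 (ITT), Tables 2.23, 2.24, 2.31 and 2.32 (per protocol), and Listings 49 to 52. The descriptive statistics listed in SAP Section 7 carry no confidence interval. This model is therefore the SAP text's stated source of an interval by arm for maximum RNA change, the protocol's primary endpoint.

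**Working it through.** The plan gives no numerical result to reproduce. The check compares the code with the promised output and then counts what can be estimated.

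**1. What the RNA code estimates.** The inputs are the code above, cohorts of 6/6/2 in Part 1 and 6/6/6/2 in Part 2 (SAP 2.3), and post-baseline Visits 2 to 6. The fixed-effect columns are intercept + visit contrasts + dose contrasts + baseline:

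- Part 1: 1 + 4 + 2 + 1 = 8
- Part 2: 1 + 4 + 3 + 1 = 9

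The only continuous column is baseline, so the only slope in the model is on baseline RNA and not on time. Dose enters as a shift common to all visits, so no arm has a rate of its own.

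**2. What the code asks to be printed.** MODEL has no SOLUTION, CL or ALPHA=0.1; `solution` sits on RANDOM. There is no LSMEANS or ESTIMATE statement. The SAP does this properly elsewhere. The steady-state code (9.1.4.2.1) runs by treatment, leaves day continuous and requests SOLUTION, CL and ALPHA=0.1. The power-model code (9.1.4.1.1) makes the same three requests. Adding CL here without ALPHA=0.1 would give 95% limits: t(0.975)/t(0.95) = 2.228/1.812 = 1.23 times too wide at 10 df, and 2.131/1.753 = 1.22 times at 15 df.

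**3. One-value endpoints.** Nadir change is one number per participant (SAP 7.1.3), and so is CD4+ change. CD4+ change has a single visit level, so it has no visit effect. With one record each, subject and residual variance enter the likelihood only as their sum: splits of 0/0.16, 0.08/0.08 and 0.15/0.01 gave identical log-likelihoods. No time slope can be fitted.

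**4. Text against code.** The text does not list dose among the fixed effects; the code pools the arms with an additive dose term. If the text means separate fits, residual df with intercept and baseline on one record each are:

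- active arm: 6 − 2 = 4
- placebo arm: 2 − 2 = 0, so no interval exists

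**5. A conditional consequence.** Suppose all visits enter the Visit 6 RNA model and decline is linear. The dose effect is then the average of (day − 1)/(Visit 6 day − 1) over Visits 2 to 6, as a fraction of the Visit 6 effect. Over the permitted visit days:

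- Part 1: from (1+2+4+7+10)/50 = 24/50 = 0.48 to (1+3+6+9+10)/50 = 29/50 = 0.58
- Part 2: from (1+2+4+6+7)/35 = 20/35 = 0.57 to (1+3+5+6+7)/35 = 22/35 = 0.63

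**6. What the fix would deliver.** For one record per participant on dose and baseline, residual df are 14 − 3 − 1 = 10 and 20 − 4 − 1 = 15. The 90% half-width, ignoring the small covariate term, is t × SD/√n. SD 0.4 is the value in Protocol 10.1.1 for maximum RNA change at the Part 1 higher dose; using it in every arm is an assumption.

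- Active dose (n=6): 1.812 × 0.4/√6 = 0.30 in Part 1; 1.753 × 0.4/√6 = 0.29 in Part 2
- Placebo (n=2): 1.812 × 0.4/√2 = 0.51 in Part 1; 1.753 × 0.4/√2 = 0.50 in Part 2

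Allowing for the covariate, simulated normal baselines gave medians of 0.30 and 0.29 (active) and 0.52 and 0.50 (placebo). For SD 0.3 to 0.6, the active-dose figure runs from 0.22 to 0.45. None of this applies to log10 CD4+.

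**The case against.** The code is labelled an example, the SAP allows appropriate adjustments, and the table shell (EFF_T3) that would show the intended columns is not in the text reviewed. This is therefore a defect of specification and not evidence that the final tables are wrong. The adjustment clause does not cure it, however: it concerns model checking and depends on the data, whereas a missing time term and a missing interval request do not.

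Three stronger readings are tempting, and the documents do not support them:

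- **A reader might infer that no rate can exist for nadir or CD4+.** A crude one can: time to nadir is derived for every participant (SAP 7.1.3; Tables 2.5 and 2.6), and the CD4+ interval is fixed. What stands is that the SAP defines no such rate and its model cannot estimate one.
- **A reader might infer a flat contradiction over fitting by treatment.** The phrase could mean with a treatment factor, as in the code. Leaving dose out of the listed fixed effects, and using BY TREATMENT for separate fits in 9.1.4.2.1, points the other way without settling it.
- **A reader might infer that the code shrinks the Visit 6 effect to 0.48–0.63 of its size.** Nothing says all visits enter that model. With Visit 6 records only, there is no dilution, and linear decline is an assumption.

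There is also a partial safeguard. Figures 2.1 and 2.2 plot RNA change by arm and visit with t-based 95% limits. They cover the Visit 6 RNA change, but not nadir or CD4+.

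**Conclusion.** The point holds as a fault in the written specification, worth correcting at modest priority. The code in 7.1.3.1 and 7.3.1.4 cannot return the stated slope and 90% CI. For nadir and CD4+ change, the visit and separate subject terms cannot be estimated. These conclusions follow from the code and the schedule and need no assumed values. The 0 df for placebo depends on reading the text as separate fits.

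The consequences are limited. No formal hypothesis is tested (SAP 2.4), and descriptive Tables 2.3 and 2.4 and Figures 2.1 and 2.2 are unaffected. The dose-response and exposure-response models and the interim Go/No-Go rule do not use this model. Tables 2.23, 2.24, 2.31 and 2.32 are produced only if participants are excluded from the per-protocol population.

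**What to change.** For nadir change, Visit 6 RNA change and CD4+ change, use one record per participant within each part: `MODEL chg = dose baseline; LSMEANS dose / CL ALPHA=0.1`, with dose in CLASS. Drop visit, the random subject effect and the by-treatment wording. Report the adjusted mean change and 90% CI per dose in place of a slope or rate.

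If an RNA rate is also wanted, specify it separately: log10 RNA from Day 1 to Visit 6 on continuous day, by treatment, labelled as an average linear rate. Its interval should allow participants to decline at different rates, for example the mean of the per-participant slopes with a t-based 90% CI. A random intercept alone assumes one common slope per arm.

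Reword the summary measures in 7.1.2 and 7.3.1.2, and align the table and listing titles with the option chosen. An RNA title may keep its rate wording only if the rate analysis is adopted.

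The cost is wording in four SAP sections (7.1.2, 7.1.3.1, 7.3.1.2, 7.3.1.4), two code blocks and the affected titles, with no new data. Intervals stay wide, above all for placebo with 2 participants per part (2 − 1 = 1 df for a mean of per-participant slopes). A straight line may also fit a lagged or curved decline poorly.

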9.1.4.2. Steady State**9.1.4.2.1. Statistical Methodology Specification**

The following pharmacokinetic statistical analyses will only be performed if sufficient data is available (i.e. if participants have well defined plasma profiles). Statistical model will be fitted for Part 1 and Part 2 respectively.

Endpoint / Variables

 Plasma primary PK endpoints include Visit 2 to visit 6 Pre-dose concentrations C_0 and visit 5 C_{τ}
Model Specification

 To assess the achievement of steady state with the pre-dose concentrations between Visit 2~6 for each treatment. A linear mixed model using Day as fixed effects and subject as a random effect on the ln-transformed pre-dose values will be performed evaluating whether steady state was achieved using Helmert transformation approach. The comparison will begin with Visit 2~6 then Visit 3~6, etc. The estimate and 90% CI of the slope for the day will be presented for the comparison(s).
Model Checking & Diagnostics

 Model assumptions will be applied, but appropriate adjustments may be made based on the data. Statistical analysis of steady state will be analyze using Helmert transformation approach.
Model Results Presentation

Code will be separated for Part 1 and Part 2 due to the different study design of the two parts. Example SAS Code for Part 1: PROC MIXED; BY TREATMENT; WHERE (DAY IN (2,3,4,5,6,7,8,9,10,11)); CLASS SUBJECT; MODEL LOGCTAU = DAY/CL ALPHA=0.1 SOLUTION; RANDOM INTERCEPT/SUBJECT=SUBJECT TYPE=UN; RUN;

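### The example code for the modelled HIV-1 RNA and CD4+ endpoints asks for an unstructured covariance matrix across participants, so its treatment standard errors and 90% CIs are not determined by the data

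*SAP*

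**What the plan says.** SAP 7.1.3.1 names two modelled endpoints on the log10 scale: HIV-1 RNA change from baseline to nadir, and change from baseline to Visit 6. Its prose has "subject fitted as a random effect", with baseline and visit as fixed effects. The example code beneath it has three relevant lines: "class dose visit subjid", "model chgRNA = baseRNA visit dose" and "random subjid / type=un solution". SAP 7.3.1.4 uses the same RANDOM statement for CD4+ change.

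SAP 7.1.3 adds: "Statistical models will be fitted separately for Part 1 and Part 2". SAP 2.3 gives the sizes: "Part 1 will include approximately 14 randomized participants" and "Part 2 will include approximately 20 randomized participants".

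The steady-state model in SAP 9.1.4.2.1 is written differently: "RANDOM INTERCEPT/SUBJECT=SUBJECT TYPE=UN". There the subject is declared, so TYPE=UN applies to a block of one element.

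The results feed Tables 2.7 and 2.8 (HIV-1 RNA), 2.15 and 2.16 (CD4+), the per-protocol counterparts 2.23, 2.24, 2.31 and 2.32, and Listings 49 to 52.

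**The concern.** In PROC MIXED, a RANDOM statement without SUBJECT= treats the whole data set as one block. With the subject identifier in CLASS there is one random coefficient per participant, and TYPE=UN gives every participant a separate variance and every pair of participants a separate covariance. The prose calls for a single variance shared by all participants.

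The data hold only one realisation of the vector of participant effects, so they cannot inform such a matrix. In particular, a random shift shared by everyone in one arm cannot be told apart from that arm's fixed effect. The model may therefore carry any amount of such shared variance, and the standard error of the treatment effect moves with it.

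A second problem lies in the prose as well. Nadir change gives one value per participant. CD4+ is measured after baseline only at Visit 6 (SAP 13.3.1). With one row per participant, a random subject effect and the residual are the same quantity.

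At stake are the modelled precision statements for the primary HIV-1 RNA endpoints and the exploratory CD4+ endpoint.

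**Working it through.** The SAP gives no parameter count, so there is no stated figure to reproduce.

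**Inputs.** Part 1 has 14 participants (6 + 6 + 2) and Part 2 has 20 (6 + 6 + 6 + 2), from SAP 2.3. HIV-1 RNA is scheduled at every clinic visit: Visits 2 to 6 give five post-baseline values to Visit 6. Over the whole schedule there are eight post-baseline visits in Part 1 and six in Part 2 (SAP 13.2).

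**Parameters requested.** An unstructured matrix for n participants has n(n+1)/2 parameters.
- Part 1: 14 × 15/2 = 105 (14 variances, 91 covariances), plus one residual = 106.
- Part 2: 20 × 21/2 = 210 (20 variances, 190 covariances), plus one residual = 211.
- One six-participant arm fitted alone: 6 × 7/2 = 21, plus one = 22.
- The prose model: 2.

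**Observations available.**

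| Fit | Nadir | Visits 2–6 | All post-baseline visits |
|---|---|---|---|
| Part 1 pooled | 14 | 14 × 5 = 70 | 14 × 8 = 112 |
| Part 2 pooled | 20 | 20 × 5 = 100 | 20 × 6 = 120 |
| One arm of 6 | 6 | 6 × 5 = 30 | 48 (Part 1) or 36 (Part 2) |

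**Identifiability.** REML uses only contrasts free of the fixed effects. If p fixed effects vary between participants, then n − p participant-level contrasts remain and at most (n − p)(n − p + 1)/2 elements of the matrix can be informed. Repeated visits add one for the residual.
- Part 1, p = 4 (intercept, baseline, two dose terms): 10 × 11/2 = 55, plus 1 = 56 of 106.
- Part 2, p = 5: 15 × 16/2 = 120, plus 1 = 121 of 211.
- One arm, p = 2: 4 × 5/2 = 10, plus 1 = 11 of 22.

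A numerical calculation of the REML information matrix gave the same ranks: 56, 121 and 11. They were unchanged when visits after Visit 6 were added (checked at eight visits in Part 1 and for the single arm, six in Part 2). More visits do not repair the deficit.

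**Effect on the standard error.** Assume, for illustration, a between-participant SD of 0.4 and a residual SD of 0.2 log10, with five complete visits. Ignoring the baseline covariate, the variance of the difference between two arms of six is (0.16 + 0.04/5) × (1/6 + 1/6) = 0.056, so the standard error is 0.24. Now add a constant c to every element of one arm's 6 × 6 block, which TYPE=UN permits. The variance becomes 0.056 + c:
- c = 0.1: standard error 0.40
- c = 1: standard error 1.03
- c = 10: standard error 3.17

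In a simulated Part 1 data set with the baseline covariate included, the REML likelihood and the dose estimate were identical for all four matrices, while the standard error ran from 0.24 to 3.17. Part 2 behaved the same way (0.25 to 3.17). The data do not choose among these values.

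**Prose model.** With one subject variance and one residual, the information rank is 2 of 2 for Visits 2 to 6 in both parts. For one row per participant it is 1 of 2.

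**The case against.** The strongest reply is that the fault sits in text labelled as example code, while the model specification is a plain random subject effect. For repeated visits that stands: the prose model is estimable and the correction is a syntax repair. It does not rescue nadir or CD4+ change, where the prose model is itself confounded.

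A reader might infer that the model will fail to converge. No PROC MIXED run supports that, and software may well print a result. What is supported is that the covariance parameters have no unique estimate.

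A reader might also infer that there are always more parameters than observations. That holds for pooled fits to Visit 6 (105 against 70; 210 against 100). It fails in Part 1 if every visit enters (105 against 112), and for Visits 2 to 6 if the SAP's phrase about fitting by treatment means one fit per arm (21 against 30). The identifiability argument does not need the count.

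Not every printed quantity is affected. With complete data, a contrast between visits within participants depends on the residual alone, and in the simulated example its standard error did not change with the matrix. What is undetermined is the precision of the intercept, the treatment means and the treatment differences.

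The consequences are also limited. SAP 2.4 says that no formal hypotheses are tested. The protocol's efficacy analysis (10.3.2.2) is descriptive, and Tables 2.3 and 2.4 do not use this code. The Part 1 decision followed a separate Bayesian rule (Protocol 10.3.1), and the dose-response and exposure-response models are separate (SAP 10 and 11).

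Finally, a reader might infer that an unblinded team would be free to pick a covariance structure. For repeated visits the prose already fixes it, so this adds little. For nadir and CD4+ change, the only guidance is that adjustments may be made once the data are seen.

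**Conclusion.** The point holds as a defect in the code for the modelled endpoints, and in the prose too for nadir and CD4+ change. As coded, 105 (Part 1) or 210 (Part 2) covariance parameters are requested when arms are pooled, where one subject variance was intended; the data can inform at most 56 of 106 and 121 of 211 parameters, residual included. Treatment standard errors and 90% CIs taken from this code into Tables 2.7, 2.8, 2.15 and 2.16 and their per-protocol versions would be arbitrary.

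The documents do not support going further, to the view that the primary analysis cannot be run or that the trial's decisions rest on this line. The descriptive summaries of maximum change stand, no test depends on the model, and the Part 2 doses were already set when the SAP was written (SAP 3.1).

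The counts assume exactly 14 and 20 participants, which the SAP gives as approximate. The count changes with enrolment; the lack of identifiability does not. The standard-error illustration rests on assumed SDs of 0.4 and 0.2.

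**What to change.** - **Repeated visits up to Visit 6:** replace the statement with `random intercept / subject=subjid;`, the form already used in SAP 9.1.4.2.1.
- **Nadir change and CD4+ change:** remove RANDOM and VISIT, and fit an ANCOVA on baseline and dose. Amend the prose in 7.1.3.1 and 7.3.1.4 to match.
- **Change to Visit 6:** state which analysis is meant. If a rate is intended, as the summary measure in SAP 7.1.2 suggests, keep the repeated-visit model. If only the single Visit 6 value is analysed, use the ANCOVA and relabel the summary measure as an adjusted mean change, because an ANCOVA does not estimate a rate.
- **CD4+ summary measure:** make the same relabelling in SAP 7.3.1.2 and in the titles of Tables 2.15, 2.16, 2.31 and 2.32, which also call it a mean rate.

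The cost is a few lines of SAP code and matching text. No extra data, visits or participants are needed.
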